## i

## Option 1

## Describe how your study meets these criteria:

a) The only record linking the participant and the research would be the consent document:

b) The principal risk would be potential harm resulting from a breach of confidentiality (i.e., a study that involves subjects who use illegal drugs).

Under this option, each participant (or legally authorized representative) must be asked whether (s)he wants to sign a consent document; if the participant agrees to sign a consent document, only an IRB approved version should be used.

## Option 2

## Describe how your study meets these criteria:

a) The research presents no more than minimal risk to the participant:

b) Involves no procedures for which written consent is normally required outside of the research context (i.e. a cover letter on a survey, or a phone script):

## Option 3

## Describe how your study meets these criteria:

a) The subject (or legally authorized representative) is a member of a distinct cultural group or community in which signing forms is not the norm.

b) The research presents no more than minimal risk to the subject.

c) There is an appropriate alternative mechanism for documenting that informed consent was obtained.

#### STUDY PERSONNEL

Do you have study personnel who will be assisting with the research? After selecting 'Yes' or 'No' you must click the 'Save Study Personnel Information' button.

∉Yes ⊂ No

#### Background

Include a brief review of existing literature in the area of your research. You should identify gaps in knowledge that should be addressed and explain how your research will address those gaps or contribute to existing knowledge in this area. For interventional research, search PubMed and ClinicalTrials.gov for duplicative ongoing and completed trials with same condition and intervention(s).

Spinal cord injury (SCI) is associated with devastating personal burdens including paralysis, sensory changes, autonomic dysfunction, and chronic debilitating pain. Few effective treatments have been developed with standard of care consisting of state-of-the-art neurocritical care, timely surgical decompression, and rehabilitation. While a variety of novel neuroprotective and neuroregenerative approaches have been posited, clinical trials to date have failed to demonstrate associated clinical benefits.

Current therapies are primarily aimed at reducing secondary injury processes, which are related to inflammation and ischemia, that persist over days-to-weeks following the primary mechanical insult. Intraparenchymal progressive hemorrhagic necrosis and swelling within the restrictive physical barrier of the pial and dural layers leads to further compression and ischemia, propagating the secondary injury cascade.

Early surgical bony decompression following SCI is thought to improve clinical outcomes, specifically after cervical-level injuries.[1, 2] While few developments have been made in actual surgical techniques beyond bony decompression, early reports suggest that reduction of intraspinal pressure (ISP) could reduce secondary injury.[3, 4] Long-recognized but not clinically employed techniques to reduce ISP involve fashioning a dorsal midline myelotomy to allow for intramedullary decompression of hematoma and necrotic tissue and expansion of the dural compartment by opening the dura and sewing in of an expansive patch.

Interestingly, corollary techniques have long been standard-of-care following cranial trauma: removal of the calvarial bone, evacuation of hematoma, expansive dural closure, and treatment of intra-cranial pressure have been proven effective in several randomized clinical trials.[5]

Each of these steps are also at times used in other domains of spinal surgery, specifically oncologic resections. Despite having been demonstrated as an option to manage spinal trauma by Allen over a century ago, [6] these techniques have not been widely studied or applied in modern spinal surgery.

The data obtained from this study will be used to inform and advance the practice of spinal cord decompression and cell-based therapies following acute SCI. Information on microsurgical technique adjustments, neurocritical nursing care standards, medical management, and ISP metrics may prove invaluable in advancing the feasible and safe aspects of these interventions.

SCI is a severely disabling neurological condition leading to impaired mobility, pain, and autonomic dysfunction. As potentially neuroprotective strategies, dorsal myelotomy and expansive duraplasty (DMED) along with cell-based therapies (e.g., autologous nerve tissue graft implantation, ANGI) are recognized as promising candidates to promote functional recovery. However, no trials of these therapies in patients have yet provided reproducible evidence of clinical efficacy, challenged by small effect sizes, low immune suppression, and low sensitivity study designs.

This pilot study design represents the first stage of a systematic evaluation of DMED +/- ANGI performed in the early/acute phase after SCI. Performance of DMED at early timepoints is expected to have the greatest impact on minimizing the deleterious effect of increased ISP and secondary injury due to PHN, which is known to be ongoing over the first hours and days after SCI. Assessment of the feasibility and safety of performing DMED +/- ANGI represent a critical first step prior to engaging in any larger-scale multicenter evaluations of efficacy.

Future larger-scale phases of the study will focus on elucidating the efficacy of these interventions in protecting against secondary neuronal injury processes and in improving function after SCI. The pilot data generated from this study will prove crucial in seeking a larger award from the National Institutes of Health (NIH) and other funding sources.

While refinements and combined therapies may prove useful, widespread clinical translation of currently employed cell transplantation protocols will likely face critical logistic and safety-related obstacles, particularly in the most opportune acute phase after SCI. The need for cell culturing and concomitant immunosuppression are fraught with potential complications, especially considering the relative immune compromised state and elevated risk of infections in the acute phase after SCI that can independently negatively impact neurological outcomes.[7]

As such, evaluation of the feasibility and safety of an autologous cell-based implantation paradigm that does not require cell culturing or concomitant immunosuppression appears ideal. Fortuitously, an autologous nerve grafting paradigm has already been established at the University of Kentucky in patients with Parkinson's disease undergoing deep brain stimulator placement.[8, 9]

Significance: There are currently no standard of care neuro-protective strategies for the treatment of acute traumatic SCI. Methylprednisolone is no longer considered standard of care based on its dubious clinical benefit combined with its demonstrated adverse effect on immune function.[14] The sodium-channel blocker, Riluzole, was recently evaluated in a phase 3 trial of 193 patients by the NACTN group.[15, 16] While safety data appeared favorable, efficacy in improving neurologic outcomes was not shown. Other potential therapies are either at the pre-clinical or early pilot stage.[17]

Progressive hemorrhagic necrosis (PHN) represents an increasingly well-characterized early mechanism of secondary injury that negatively impacts neurologic outcomes. Structural failure of the integrity of intramedullary capillaries, so called 'capillary fragmentation' is thought to underlie this acute and dynamic secondary injury process. Animal studies modeling contusional SCIs across different laboratories have revealed a 2-2.5-fold increase in extravasated intramedullary blood within the first 12-24 hours following blunt impact trauma. [18-20]

As such, given the direct linkage between distinct microscopic hemorrhages within the cord and the progressive secondary injury and neurologic deterioration following SCI, it is no surprise that PHN has long been deemed a potential target for therapy dating back over a century.[6] In addition to the parallel PHN induced secondary injury processes involving oxidative stress and the release of toxic substances like heme degradation products, it is noteworthy that PHN also leads to intradural mass effect related to progressive spinal cord swelling, a process that is directly proportional to the severity of the impact. Since early reports suggesting that dorsal myelotomy, a longitudinal midline incision in the spinal cord, together with the removal of "contused tissue were beneficial in injured dogs and humans, only occasional reports of animal studies have shown proof of the benefits from hemorrhagic necrosis removal.[21, 22]

Besides simply allowing for unhindered spinal cord swelling and improvement in intraspinal pressures, DMED also allows an opportunity for an assessment of the potential supplemental and even synergistic effects of cell-based therapies in modulating the local microenvironment after SCI. Implantation of growth-factor producing cells or stem cells has been validated in numerous preclinical models of CNS injury and neurodegeneration.[23-26]

More recently, small-scale evaluations of cell-based therapies have been undertaken at various stages after SCI with reassuring safety profiles.[27] However, several important practical limitations have been noted with these protocols that significantly limit the potential for widespread and safe use of cell implantation in the early post-traumatic setting. Most critically, the need for cell culturing and concomitant immunosuppression introduce significant logistic and safety-related considerations, especially considering the relative immune compromised state and elevated risk of infections in the acute phase after SCI that can independently negatively impact neurological outcomes.[7]

As a way to bypass these obstacles, ANGI represents a unique cell-based therapy that can allow for prompt intervention at the injury site without the need for immunosuppression.

Fortuitously, neurosurgery and neuroscience colleagues at the University of Kentucky have already established and validated a reproducible source of cellular tissue from the peripheral nervous system,[8, 9] that contain injured-peripheral nerve tissues shown to include a variety of cells that express several key growth factors and repair molecules including glial cell line-derived neurotrophic factor, brain-derived neurotrophic factor, nerve growth factor, and neurotrophin-3. They have implanted ANGI in to the CNS of 80 participants without any serious adverse events related to the study intervention and with the most common study-related adverse event being paresthesias and acute pain at the lateral aspect of the foot and ankle ipsilateral to the biopsy. Amongst other possible cellular neurotrophic sources 9 contained within these grafts, Schwann cells are known to transdifferentiate after injury into an activated repair phenotype through a c-Jun mediated pathway and produce a host of repair and survival promoting neurotrophins and anti-apoptotic factors.[28]

## Objectives

List your research objectives. Please include a summary of intended research objectives in the box below.

Specific Aim 1: Assess whether dorsal myelotomy and expansive duraplasty (DMED) after cervical acute traumatic SCI, performed either without or with autologous nerve graft implantation (ANGI), is safe and feasible (n = 5 each)

Safety: Vital signs, clinical examination findings, and clinical laboratory results will be carefully and continuously monitored during the course of hospitalization. Adverse events (AEs) will be assessed throughout the course of hospitalization through Day 28.

Feasibility: To assess the feasibility of running a larger phase II or III study among this population of patients where treatment must begin within the acute time frame. The number of patients who would otherwise be eligible for the study but did not receive study treatment within the 48-hour time frame (ratio of recruited versus screened) and the rate of recruitment (recruited versus eligible) will be recorded. As part of assessing the procedural feasibility, the number of participants who enrolled and received DMED and who received ANGI will be recorded. To assess the compliance feasibility of the study, the number of participants attending each follow-up visit will also be summarized.

Specific Aim 2: Assess whether intraspinal pressure and metabolism can be reliably measured in real-time after dorsal myelotomy and expansive duraplasty, performed either without or with autologous nerve graft implantation (n =5 each). Participants will be monitored in the neurointensive care unit for 7 days or longer (as needed) postoperatively.

Prior to study initiation, ICU personnel will be trained on all study protocols along with the assistance of the nursing manager / educator. Clinical exams, as part of the standard of care, including International Standards for Neurological Classification of Spinal Cord Injury (ISNCSCI) motor scores, will be obtained daily until day 7, then weekly while admitted. ISP will be monitored in real-time with a commercially available indwelling intradural microsensor. [4] Cerebrospinal fluid for microdialysis will be obtained days 1-4, and 7. [3, 12]

Specific Aim 3: Preliminarily assess whether ANGI, in addition to DMED impacts intraspinal pressure and metabolic measurements.

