#### **Research Procedures**

Describe how the research will be conducted.

- What experience will study participants have?
- What will study participants be expected to do?
- · How long will the study last?
- Outline the schedule and timing of study procedures.
- · Provide visit-by-visit listing of all procedures that will take place.
- Identify all procedures that will be carried out with each group of participants.
- Describe deception and debrief procedures if deception is involved.

Differentiate between procedures that involve standard/routine clinical care and those that will be performed specifically for this research project. List medications that are explicitly forbidden or permitted during study participation.

We propose that intraspinal pressure management starting at the time of surgical decompression following acute SCI alone, or with ANGI, may ultimately provide a meaningful impact to improve functional outcomes and quality of life. As a first step, we propose to systematically assess the safety and feasibility in this at-risk patient population. We will perform dorsal myelotomy to promote hematoma and necrosis evacuation for patients that have sustained severe acute cervical / thoracic SCI. This will be performed along with expansive duraplasty during standard surgical (bony) decompression with or without autologous nerve graft implantation (ANGI) in 5 participants each (n = 10 total). As a cell-based therapy, ANGI allows for a unique opportunity for prompt intervention at the injury site without the need for immunosuppression.

As part of research, participants will have intrathecal pressure probes and microdialysis catheters inserted at the time of surgery. Each participant will undergo a pre-operative MRI to inform the extent of decompression and dural expansion, and a post-operative MRI on day 2 to confirm that surgical goals were achieved. Continuous monitoring of intraspinal pressures, biochemical profiles, adverse events, ASIA impairment scores, and functional independence measures will be performed from the neurointensive care unit to one year postoperatively.

Screening and Registration Procedures - Participants with suspected acute cervical or thoracic SCI will be screened upon arrival to hospital. As part of the standard of care, these evaluations will occur prior to enrollment:

- Vital signs (Temperature, Blood Pressure, Respiration rate, Pulse, O2 saturation, Height, Weight)
- Physical examination and Medical History

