Probe / Catheter Insertion: The ISP probe and microanalysis catheter will be inserted in the operating room. During the standard-ofcare posterior approach, a 14-gauge introducer will be used to separately tunnel an FDA-approved pressure probe (e.g., Codman Microsensor Transducer®, Integra LifeSciences, Princeton, NJ) and an FDA-approved microdialysis catheter (e.g., M dialysis AB, North Chelmsford, MA) intradurally one level below the injury over the surface of the injured cord and tunneled up to the site of maximal cord swelling as noted on the preoperative MRI study.[4] The ISP probe will be calibrated and it along with the catheter will be advanced subdurally, under the operating microscope, through the dural hole until their tips lie at the site of maximal spinal cord swelling according to the MRI scan. The separate slit dural openings will be covered with fibrin glue (e.g., Tisseel®, Baxter, Deerfield, IL). Standard-of-care postoperative CT studies (when available) will be used to confirm in situ probe positioning.

Intraspinal Pressure and Arterial Blood Pressure Monitoring: The pressure catheter will be connected to a Codman ICP Express monitoring device linked via a ML221 amplifier to a PowerLab running LabChart (AD Instruments, Colorado Springs, CO). Standard-of-care continuous arterial blood pressure monitoring will be performed through a radial arterial line, in turn also connected to the PowerLab system. ISP and blood pressure signals are sampled at approximately 1 kHz, and patients are monitored for up to 7 days following SCI. Data will be analyzed using Labchart (AD Instruments, Colorado Springs, CO) and ICM+ (www.neurosurg.cam.ac.uk/icmpl us). Spinal cord perfusion pressure will be calculated as mean arterial pressure (MAP) – ISP. Of

(www.neurosurg.cam.ac.uk/icmpl us). Spinal cord perfusion pressure will be calculated as mean arterial pressure (MAP) – ISP. Of note, ISP will be expected to be different from intrathecal pressure (typically measured in the lumbar spine) as the swollen, injured cord is compressed against the dura thus compartmentalizing the intrathecal space.[29]

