Microdialysis (MD) Setup and Analysis: Microdialysis will be initiated postoperatively in the neurointensive care unit in all enrolled subjects.[12] Central nervous system fluid will be perfused at 0.3 µL/min using the 106 microdialysis pump (M dialysis AB). MD vials will be changed hourly and analyzed using ISCUSFlex (M dialysis AB) for glucose, lactate, and pyruvate. The lactate-to-pyruvate ratio will be calculated. The first two samples from each subject will be discarded to allow priming of the MD catheter and stabilization of the metabolite concentrations. Metabolite levels will be

compared to corresponding hourly averages of ISP, MAP, and SCPP. As noted by other authors [12], we expect that such a MD protocol will measure spinal cord surface metabolism at the injury site, which is thought to correlate with intraparenchymal injury site metabolism.[30]

Post-treatment follow-up: After surgery, subjects will be followed in the neuro intensive care unit and throughout their hospital stay per routine, standard-of-care clinical guidelines for the management of acute SCI. Following hospital discharge, subjects will then undergo assessments in accordance with the study calendar.

Post-treatment follow-up: Day 28 (± 7 days), Day 42 (± 7 days)

Review unresolved AEs

- Record additional AEs/SAEs
- ASIA Impairment Scale

Post-treatment Follow-up: Day 84 (± 14 days), Day 182 (± 14 days) and Day 365 (± 30 days)

- Review unresolved AEs
- Record additional SAEs
- ASIA Impairment Scale
- Spinal Cord Independence Measure (vIII)

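### Do the microdialysis sampling days clash with hourly vials and with a pressure-monitoring window counted from injury?

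*Protocol*

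**What the plan says.** Under Objectives, Specific Aim 2 asks whether intraspinal pressure (ISP) and metabolism can be measured reliably in real time. It gives the sampling days: "Cerebrospinal fluid for microdialysis will be obtained days 1-4, and 7". It says of the intensive-care stay: "Participants will be monitored in the neurointensive care unit for 7 days or longer (as needed) postoperatively".

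Under Research Procedures, the microdialysis paragraph gives the start: "Microdialysis will be initiated postoperatively in the neurointensive care unit in all enrolled subjects". It gives the interval: "MD vials will be changed hourly and analyzed using ISCUSFlex (M dialysis AB) for glucose, lactate, and pyruvate". It also gives the priming rule: "The first two samples from each subject will be discarded to allow priming of the MD catheter". Metabolite levels are then to be "compared to corresponding hourly averages of ISP, MAP, and SCPP", where MAP is mean arterial pressure and SCPP is spinal cord perfusion pressure.

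The pressure-monitoring paragraph of the same section says: "ISP and blood pressure signals are sampled at approximately 1 kHz, and patients are monitored for up to 7 days following SCI". The opening of the section has one sentence with a longer span, which lists what is followed without interruption: "intraspinal pressures, biochemical profiles, adverse events, ASIA impairment scores, and functional independence measures will be performed from the neurointensive care unit to one year postoperatively". The screening text allows study procedures up to 48 hours after injury. A Table of Events is attached to the section but is not part of the text available here.

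**The concern.** Two things look unreconciled.

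- **Sampling days.** Aim 2 names five days and skips days 5 and 6. The procedures describe hourly vials and mention neither a gap nor an end. Read in isolation, the second text could mean an unbroken run.
- **Time origin.** ISP is counted from injury, while microdialysis begins after surgery. If the listed days are postoperative, the two windows slide apart as the delay to surgery grows, and ISP could end before the day-7 vials are drawn.

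If both held, staff would lack one rule for when vials are due, and day-7 vials would drop out of the hourly comparison with ISP according to surgical delay. In a comparison of 5 against 5, unequal delays would also mean that ISP is observed over different postoperative hours in different participants. Completeness, a feasibility measure, would depend on which count of expected vials was used.

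**Working it through.** The protocol gives no vial count to reproduce, so the check is one of overlapping time windows.

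**Inputs from the protocol:** listed days 1 to 4 and 7; hourly vials; first two discarded; ISP for up to 7 days (168 h) from injury; delay t from injury to surgery between 0 and 48 h.

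**Assumptions, not in the protocol:** 24 vials per sampling day; ISP runs its full 168 h; where an unbroken run is considered, it lasts 7 days.

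**Vials retained if nothing is lost**
- Five listed days: 5 × 24 − 2 = 118.
- Unbroken 7 days: 7 × 24 − 2 = 166.

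**Reading A: days counted from surgery, day 1 = first 24 h.** ISP ends at postoperative hour 168 − t. Day 7 is postoperative hours 144 to 168. Day-7 hours with ISP = max(0, 24 − t).

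| t (h) | Day-7 hours with ISP | Pairs, listed days | Pairs, unbroken 7 days |
|---|---|---|---|
| 0 | 24 | 118 | 166 |
| 12 | 12 | 96 + 12 − 2 = 106 | 156 − 2 = 154 |
| 24 | 0 | 96 − 2 = 94 | 144 − 2 = 142 |
| 48 | 0 | 96 − 2 = 94 | 120 − 2 = 118 |

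The largest losses are 24/118 = 20.3% on the listed days and 48/166 = 28.9% for the unbroken run. At t = 24 h the unbroken run loses 24/166 = 14.5%.

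**Reading B: days counted from injury, day 1 = first 24 h.** Day 7 is hours 144 to 168 after injury, inside the ISP window, so 24 of 24 hours are covered for every t. Vials cannot precede surgery, so some early listed hours do not exist: 120 − 24 − 2 = 94 vials at t = 24 h and 120 − 48 − 2 = 70 at t = 48 h. Every vial that is drawn has its ISP value.

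**Reading C: day 0 = the first 24 h, on either clock.** Day 7 then starts at hour 168, and a strict 168 h ISP limit from injury leaves no overlap for any t. This would make every day-7 pairing impossible by design, which is hard to credit in a plan that names day 7 for sampling and 7 days for monitoring.

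**How often Reading A would bite fully.** The protocol cites a study in which 94.6% were decompressed within 24 h. If that held here, (1 − 0.946) × 10 = 0.54 participants would lose all of day 7. The others would lose t hours of it.

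The result turns wholly on the day convention, which the available text does not state.

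**The case for a change.** The best case for acting is that sampling days and time origin are rules for collecting data. A vial that was never drawn cannot be recovered at analysis, and an unseen analysis plan would not help. The same 118 vials would also be 100% complete against the listed days but 71% (118/166) against an unbroken week. Counting from injury only moves the loss to the early hours.

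Part of this stands. No day origin is printed in the available text, and the microdialysis paragraph does not repeat the days. The rest weakens on reading the passages together.

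- Aim 2 supplies the days, the gap and the last day. The procedures supply the interval and the start. Hourly vials on the five listed days satisfies both, and it fixes the expected count at 118.
- The procedures say when microdialysis begins, not that the listed days are numbered from surgery.
- The sentence on 7 days or longer concerns the stay in intensive care and sets no ISP duration. The sentence running to one year covers a list that includes functional measures followed to Day 365, and it can describe the span of the whole list.
- The ISP limit is a ceiling, so records of unequal length are already expected.
- Hours lost before surgery under Reading B follow from any count that starts at injury. They are not a pairing failure.

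A tighter rule for Aim 3, confining the arm comparison to hours that every participant contributes, is no clear gain. With 10 participants, one early probe failure would shorten the comparison for all. Rewording the discard rule changes nothing, because samples are already defined by the hourly vial change.

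**Conclusion.** The concern does not call for a change. The text is silent on a day origin but does not contradict itself on the sampling days. A loss of day-7 pairs arises only if the listed days are postoperative (or, on either clock, are numbered from day 0) and ISP stops strictly 168 h after injury. With day 1 as the first 24 postoperative hours, the listed-day loss runs from nothing at t = 0 to 24 of 118 pairs (20.3%) at t of 24 h or more. With days counted from injury and day 1 as the first 24 h, no vial lacks ISP.

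Even on the unfavourable reading, days 1 to 4 keep their pairs, and day-7 vials still inform metabolism. Aims 2 and 3 concern the measurability of ISP and metabolism and the effect of the graft on each. Neither aim requires paired hours. The pairing appears only in the microdialysis paragraph.

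Staff and analysts would sensibly settle the day origin and stop time from the Table of Events or with the investigators, who review missed events monthly under Data and Safety Monitoring. This conclusion assumes that the Table of Events does not impose the unfavourable combination. It takes no position on how long monitoring should last.
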